7.9. Study Assessments

The Schedule of Assessments is shown in Table 7. Pretreatment, treatment, and follow-up procedures are detailed in Sections 7.9.1 through 7.9.5.

Version 1.0 Page 53 of 145

Table 7: Schedule of Assessments

Evaluation or Procedure	Pretrea	tment							Cycle	e 1						
Study Day	Screen (-28 to -2)	Day -1	1	2	3	8	9	10	15	22	29	36	37	38	39	40 ± 2
Informed consent	X															
NETSPOT Gallium 68 dotatate PET/CT scan ^{a,b}	X															X
Review of inclusion/exclusion criteria	X															
Collection of FFPE tumor sample/slides	X															
Record tumor genetic information	X															
Inpatient status ^{c,d}		X	X	X	X	X	X	X				X	X	X	X	
XmAb18087 administration ^{e,f}			X			X			X	X	X	X				
Pembrolizumab administration ^f									X							
Medical history ^g	X	X														
Demographics	X															
Physical examination ^{g,h}	X	X		X	X	X	X	X	X	X	X	X				X
Neurologic examination ⁱ		X														
Vital signs ^{c,j,k}	X	X	X	X	X	X	X	X	X	X	X	X	X	X	X	
Height		X														
Weight		X	X			X			X	X	X	X				
ECOG performance statush	X	X	X			X			X	X	X	X				
12-lead electrocardiogram (supine) ^{l,m}	X	X	X			X	X		X	X	X	X				
CBC w/ differential (absolute and percentage), platelet count ^h	X		X	X	X	X	X	X	X	X	X	X				
Chemistry panel ^h	X		X	X	X	X	X	X	X	X	X	X				
Coagulation panelh	X		X	X		X		X	X	X	X	X				
Urinalysis	X	X		X		X		X	X	X	X	X				
HBsAg, HBcAb, HCV, HIV	X															

Version 1.0 Page 54 of 145

Table 7: Schedule of Assessments (Continued)

Evaluation or Procedure	Pretrea	itment							Cycle	: 1						
Study Day	Screen (-28 to -2)	Day -1	1	2	3	8	9	10	15	22	29	36	37	38	39	40 ± 2
Serum β–hCG (females of childbearing potential) FSH (postmenopausal) ⁿ	X	X								X						
Flow cytometry (blood) ^o			X	X	X	X	X	X	X	X	X	X	X	X	X	
Cytokine/inflammation panel ^p			X	X	X	X	X	X	X	X	X	X	X	X	X	
Polyoma virus assay (serum) ^q		X														
Biobanking sample (blood) ^{r,s}		X		X		X										X
PK blood sampling ^t		X	X	X	X	X		X	X	X	X	X	X	X	X	
Immunogenicity (ADA) blood sampling ^u		X	X			X			X	X	X	X				
RECIST 1.1 tumor assessment ^v	X															X
Monitor/record adverse events	X	X	X	X	X	X	X	X	X	X	X	X	X	X	X	X
Concomitant medications	X	X	X	X	X	X	X	X	X	X	X	X	X	X	X	X
Fresh tumor biopsy (optional) ^{s,w}	X							X								

Version 1.0 Page 55 of 145

Table 7: Schedule of Assessments (Continued)

Evaluation or Procedure			C	ycle 2 and	Higher		
Study Day	1	8	15	22	29	36	40 ± 2
NETSPOT Gallium 68 dotatate PET/CT scan ^{a,b}							X
XmAb18087 administration ^{e,f}	X	X	X	X	X	X	
Pembrolizumab administration ^f			X				
Physical examination	X	X	X	X	X	X	
Vital signs ^{j, k}	X	X	X	X	X	X	
Weight	X	X	X	X	X	X	
ECOG performance status ^h	X	X	X	X	X	X	
12-lead electrocardiogram (supine) ^{l,m}	X	X	X	X	X	X	
CBC w/ differential (absolute and percentage), platelet count ^h	X	X	X	X	X	X	
Chemistry panel ^h	X	X	X	X	X	X	
Coagulation panel ^{hl}	X	X	X	X	X	X	
Urinalysis	X			X			
Serum β -hCG (females of childbearing potential) FSH (postmenopausal) ⁿ	X			X			
Flow cytometry (blood) ^o				X		X	
Cytokine/inflammation panel ^p	X			X			
PK blood sampling ^t	X		X				
Immunogenicity (ADA) blood sampling ^{u,x}	X		X	X		X	
RECIST 1.1 tumor assessment ^v							X
Monitor/record adverse events	X	X	X	X	X	X	
Concomitant medications	X	X	X	X	X	X	

Version 1.0 Page 56 of 145

Table 7: **Schedule of Assessments (Continued)**

Evaluation or Procedure			Post-treatment	
Study Day	ЕОТ	14 d post-EOT	28 d post-EOT	Long-term Follow-up (6 & 12 mo after EOT)
NETSPOT Gallium 68 dotatate PET/CT scan ^{a,b}	X			
Medical history			X	
Physical examination	X	X	X	
Vital signs ^{i, k}	X	X	X	
Weight	X	X	X	
ECOG performance statush	X	X	X	
12-lead electrocardiogram (supine) l,m			X	
CBC w/ differential (absolute and percentage), platelet count ^h	X	X	X	
Chemistry panel ^h	X	X	X	
Coagulation panel ^h	X	X	X	
Urinalysis	X	X	X	
HBsAg, HBcAb, HCV, HIV	X			
Serum β–hCG (females of childbearing potential) FSH (postmenopausal) ⁿ	X		X	
Flow cytometry (blood) ^o	X	X	X	
Cytokine/inflammation panel ^p				
Polyoma virus assay (serum) ^q	X		X	
PK blood sampling ^t	X	X	X	
Immunogenicity (ADA) blood sampling ^{u,x}	X	X	X	
RECIST 1.1 tumor assessment ^v	X			
Monitor/record adverse events	X	X	X	
Concomitant medications	X	X	X	
Phone/email/mail contact for progression				X

Version 1.0 Page 57 of 145 Abbreviations: ADA = anti-drug antibody; β–hCG = beta unit of human chorionic gonadotrophin; CBC = complete blood counts; CT = computed tomography; EOI = end of infusion. EOT = end of treatment; ECG = electrocardiogram; ECOG = Eastern Cooperative Oncology Group; FACS = fluorescence-activated cell sorting; FFPE = fresh frozen paraffin-embedded; FSH = follicle-stimulating hormone; HBsAg = hepatitis B surface antigen; HBcAb = hepatitis B core antibody; HCV = hepatitis C virus; HIV = human immunodeficiency virus; mo = month; MRI = magnetic resonance imaging; NET = neuroendocrine tumors; PE = physical examination; PET = positron emission tomography; PK = pharmacokinetic; RECIST = Response Evaluation Criteria In Solid Tumors; SSTR2 = somatostatin

- ^a If subject has undergone NETSPOT gallium 68 dotatate PET/CT scan within 6 weeks prior to enrollment and the images and a report of results are available for collection, the scan need not be repeated at baseline. If SSTR2 radionuclide scanning and RECIST 1.1 tumor assessment by CT/MRI are planned within 2 days of each other. RECIST imaging should be conducted first.
- b NETSPOT gallium 68 dotatate PET/CT scan will be performed on Day 40 ± 2 of Cycle 1 and of every second cycle thereafter; that is, at the end of Cycle 3, Cycle 5, etc. The EOT scan will be performed only if the subject has not undergone scan within the past 2 months.
- ^c On Day -1, hospitalization is optional. Hospitalization on Days 36 through 39 in Cycle 1 is optional if PK sampling cannot be accommodated as an outpatient. Vital sign assessments on Days 36 through 39 in Cycle 1 will be performed only if the subject is hospitalized.
- d Any subject who has shown symptoms of CRS during a required inpatient hospitalization will be monitored as an inpatient for at least 24 hours after the symptoms have subsided.
- EXMAb18087 will be administered as be observed as inpatients for the first 2 doses. For all other infusions of XmAb18087, the subject will be observed for at least 4 hours following subsequent infusions, except that the observation period may be decreased to 2 hours if no infusion reactions have occurred for at least 3 consecutive infusions and the subject has completed 4 infusions at the highest dose for that subject.
- f XmAb18087 is administered on Day 15 in Parts A and C only. Pembrolizumab is administered on Day 15 of each cycle in Part B only. XmAb18087 is NOT to be administered on Day 15 in Part B. Pembrolizumab will be provided by sites as standard of care.
- g Complete medical history and PE is to be performed at Screening. For all the other time points, only an abbreviated, symptom-directed PE is to be performed.
- May be performed up to 24 hours prior to infusion. The following procedures that are completed on Day -1 within 24 hours of Cycle 1 Day 1 dosing do not need to be repeated on Cycle 1 Day 1: PE, ECOG, and local safety laboratories (eg, CBC with differential and platelets, chemistry panel, coagulation panel, and urinalysis). These safety laboratory assessments will be performed by the central laboratory and should also be performed by local clinical site laboratories so that clinical site personnel can review results before administering XmAb18087.
- Baseline neurologic examination to be performed on Day -1. If a subject appears to be experiencing neurologic toxicity, the neurologic examination should be repeated as necessary to evaluate the subject's condition. Guidelines on management of neurologic toxicity are included in both Section 11.3.3.4 and Appendix C.
- Supine blood pressure and pulse rate, body temperature, respiratory rate, and blood oxygen saturation by pulse oximetry. On days of XmAb18087 infusions, vital signs should be taken within 60 minutes of predose; 15, 30, and 60 minutes after start of infusion (± 5 minutes for each time point); immediately (within 5 minutes) before EOI; 15, 30, and 60 minutes after EOI (± 5 minutes for each time point); and then hourly (± 5 minutes) for 3 hours. When possible, vitals should be measured before blood sampling. Oxygen saturation levels will be captured with each vital sign collection; however, pulse oximetry monitoring must be maintained continuously throughout the entire admission or observation period for each administration of XmAb18087. For information on management of oxygen saturation of 90% or lower, see Section 11.3.3.1. All vital signs during infusion should be taken with the subject in the same position. On nondosing days, vitals should be measured before blood sampling.
- Non days of pembrolizumab infusions, vital signs should be taken immediately prior (within 10 minutes before blood sampling) to the start of infusion; during the infusion at 5 and 15 minutes (± 2 minutes); immediately (within 2 minutes) before the EOI; and at 15 minutes (± 2 minutes) after EOI.
- On days when XmAb18087 is infused, electrocardiograms should be taken prior to infusion, 2 to 4 hours after EOI, and if clinically indicated.
- $^{\rm m}$ $\,$ Part B only: ECGs are not performed on days when pembrolizumab is administered.

receptor 2.

- ⁿ Once postmenopausal status has been established by FSH, this test need not be repeated during the clinical trial.
- In Cycle 1, whole blood for flow cytometry (FACS) analysis will be obtained predose on Day 1 (± 1 hour); on Day 2 (24 hours post-EOI ± 3 hours); on Day 3 (48 hours post-EOI ± 3 hours); predose on Day 8 ± 1 hour; on Day 9 (24 hours post-EOI ± 3 hours); on Day 10 (48 hours post-EOI ± 3 hours); predose on Day 15 ± 1 hour; predose on Day 22 ± 1 hour; predose on Day 29 ± 1 hour; predose on Day 36 ± 1 hour; on Day 37 (24 hours post-EOI ± 3 hours); on

Version 1.0 Page 58 of 145

- Day 38 (48 hours post-EOI \pm 3 hours); and on Day 39 (72 hours post-EOI \pm 3 hours). In **Cycles 2 and higher**, whole blood for FACS will be obtained predose on Day 22 \pm 2 days and on Day 36 \pm 2 days. **Upon discontinuation from the study**, whole blood for FACS analysis should be obtained at EOT (\pm 2 days), at 14 days post-EOT (\pm 2 days), and at the 28 days post-EOT visit(\pm 2 days.)
- In **Cycle 1**, serum for cytokine profile analysis will be obtained predose on Day 1, 8, and 36 and at 5 minutes (± 1 minute), 1 hour (± 10 minutes), 2 hours (± 10 minutes), 4 hours (± 10 minutes), 7 hours (± 10 minutes), and 10 hours (± 10 minutes) post-EOI; on Days 2, 9, and 37 (24 hours post-EOI ± 3 hours), Day 3, 10, and 38 (48 hours post-EOI ± 3 hours), and on Day 39 (72 hours post-EOI ± 3 hours). Additionally, samples will be collected predose on Days 15, 22, and 29 and at 5 minutes (± 1 minute), 1 hour (± 10 minutes), 2 hours (± 10 minutes), 4 hours (± 10 minutes), and 7 hours (± 10 minutes) post EOI. In **Cycle 2 and higher**, serum for cytokine profile analysis will be obtained on Day 1 and Day 22 (± 2 days) of each cycle predose and at 1 hour (± 10 minutes), 2 hours (± 10 minutes), and 4 hours (± 10 minutes) post EOI. Serum should also be drawn at any time there is clinical suspicion of cytokine release syndrome and repeated 4 hours later.
- ^q Polyoma virus assay serum collection is for Part A and Part B only.
- ^r Including serum, peripheral blood, and nucleic acid samples.
- s Optional; by specific subject consent.
- In **Cycle 1**, serum for PK analysis will be obtained at Day -1; on Days 1 and 36 predose and at 5 minutes (± 1 minute), 1 hour (± 10 minutes), 2 hours (± 10 minutes), 4 hours (± 10 minutes), 7 hours (± 10 minutes), and 10 hours post-EOI (± 10 minutes, Day 1 only); on Days 2 and 37 (24 hours post-EOI ± 3 hours), and Days 3 and 38 (48 hours post-EOI ± 3 hours), and Day 39 (72 hours post-EOI ± 3 hours); on Day 8 predose and at 5 minutes (± 1 minute) post-EOI; on Day 10 (48 hours post-EOI); and on Days 15, 22, and 29 predose and at 5 minutes post-EOI (± 1 minute). In **Cycles 2 and higher**, serum for PK analysis will be collected on the first day of each cycle (± 2 days) predose and 5 minutes (± 1 minute) post-EOI (all subjects). Subjects in Part B only (combination therapy) will also have serum collected for PK analysis on Day 15 at predose and 5 minutes (± 1 minute) post-EOI. Upon **discontinuation from the study**, serum for PK analysis should be obtained at the EOT visit (± 2 days), the 14-day post-EOT visit (± 2 days), and the 28 day post-EOT visit (± 2 days).
- In Cycle 1, serum for ADA will be collected on Day -1 and predose (± 1 hour) on Days 1, 8, 15, 22, 29, and 36. In Cycles 2 and higher, serum for ADA analysis will be collected predose on Days 1, 15, 22 and 36 (± 2 days). Upon discontinuation from the study, serum for ADA will be collected at EOT (± 2 days), at 14 days post-EOT (± 2 days), and at 28 days post-EOT (± 2 days).
- Radiographic tumor evaluation will be performed by CT/MRI at baseline and at all other disease assessment time points. All studies for the baseline RECIST assessment should be performed within 14 days prior to the first dose of drug. The EOT tumor assessment will not be performed if the subject has had an assessment within the past 30 days.
- ^w The post-treatment fresh tumor biopsy should be performed between 12 and 21 days after first dose of XmAb18087.
- Subjects with a positive ADA at termination will be followed every 28 days (± 3 days) until ADA reverts to baseline or until the next intervening treatment.

Version 1.0 Page 59 of 145

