7.3. Dosing Schedule

Each subject will be administered XmAb18087 IV at a constant infusion rate over

Version 1.0 Page 44 of 145

The initial treatment period for each subject in this study is 1 cycle. Each cycle is 42 days long. In Part A and Part C, each cycle will consist of 6 weekly doses of XmAb18087 (on Days 1, 8, 15, 22, 29, and 36).

In Part B, each cycle will consist of 5 XmAb18087 doses on Days 1, 8, 22, 29, and 36. Pembrolizumab will be administered as 1 dose during each 42-day cycle, on Day 15.

Part A dose levels are defined in Table 2. Part B dose levels are defined in Table 3. Part C dose levels are defined in Table 4.

The dose is based on the subject's actual baseline weight measurement in kilograms (rounded to the nearest integer) on Day -1. Following the first dose at any dose level, the weight used for calculation of subsequent doses will be modified only if the subject's weight changes by more than 10% from the baseline weight, at which point the dose will be recalculated using the current weight (rounded to the nearest integer).

Version 1.0 Page 45 of 145

Table 2: Part A (MCC) Monotherapy Safety Run-in and Expansion Cohorts

					Cycle	e 1						Cycle	2+			Subjects
	Cycle and Day	D1	D8	D15	D22	D29	D36	D40	D1	D8	D15	D22	D29	D36	D40	
	•							± 2							± 2	
	Drug			XmA	b1808	7		EA			XmAb	18087			EA	
				(με	g/kg)						(μg/	kg)				
	1	8	15	22	29	36	40	43	50	57	64	71	78	82		
Part A	1A	0.3	1.0	1.0	1.0	1.0	1.0		1.0	1.0	1.0	1.0	1.0	1.0		3 - 6
(Safety	2A	0.3	1.0	2.0	2.0	2.0	2.0		2.0	2.0	2.0	2.0	2.0	2.0		3 - 6
Run-in)	3A	0.3	1.0	2.0	4.0	4.0	4.0		4.0	4.0	4.0	4.0	4.0	4.0		3 - 6
Part A (Expansion)	Expansion A							At	RD coho	rt						Up to 22

D = day; EA = efficacy assessment (no drug administered); MCC = Merkel cell carcinoma; RD = recommended dose. Maximum escalated dose for each cohort in bold.

Version 1.0 Page 46 of 145

Table 3: Part B (MCC) Combination Therapy Safety Run-in and Expansion Cohorts

	Cycle			(Cycle 1						(Cycle 2	+			Subjects
	and Day	D1	D8	D15	D22	D29	D36	D40	D1	D8	D15	D22	D29	D36	D40	
								± 2							± 2	
	Drug	XmAb (μg/		Pem (mg)	X	mAb18 (μg/kg		EA	XmAb (μg/		Pem (mg)	X	mAb18 (μg/kg		EA	
	Study Day	1	8	15	22	29	36	40	43	50	57	64	71	78	82	
	1B	0.3	0.3	400	0.3	0.3	0.3		0.3	0.3	400	0.3	0.3	0.3		3 - 6
Part B	2B	0.3	1.0	400	1.0	1.0	1.0		1.0	1.0	400	1.0	1.0	1.0		3 - 6
(Safety Run-in)	3B	0.3	1.0	400	1.0	2.0	2.0		2.0	2.0	400	2.0	2.0	2.0		3 - 6
	4B	0.3	1.0	400	1.0	2.0	2.0		2.0	4.0	400	4.0	4.0	4.0		3 - 6

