7.9.3.1. Clinical Assessments

PEs and laboratory evaluations may be performed within 24 hours prior to XmAb18087 infusion:

- Record concomitant medications and AEs (CTCAE and CRS revised grading system, Section 11.1).
- Abbreviated, symptom-directed PE, including weight
- ECOG performance status (Appendix B)
- Vital signs (Section 11.8):
 - On infusion days, time points include: within 60 minutes of predose; approximately 15, 30, and 60 minutes after start of infusion (± 5 minutes for each time point); immediately (within 5 minutes) before end of infusion (EOI; if different than 60 minutes from start of infusion); approximately 15, 30, and 60 minutes after EOI (± 5 minutes for each time point); and then hourly (± 5 minutes) for 3 hours. The pulse oximetry for blood oxygen saturation level needs to be captured with each vital sign collection; however, pulse oximetry monitoring must be maintained continuously throughout the entire admission or observation period for each administration of XmAb18087. For information on management of oxygen saturation of 90% or lower, see Section 11.3.3.1.
 - On non-dosing days, vitals should be measured before blood is drawn.
 - For subjects who tolerate 3 XmAb18087 consecutive infusions without an infusion reaction during the infusion or postinfusion observation period and who have completed 4 infusions at the highest dose for that subject, the postinfusion

Version 1.0 Page 62 of 145

observation period and vital signs assessment may be reduced from 4 hours to 2 hours.

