10.1.4. Administration of XmAb18087

XmAb18087 administration should begin as soon as possible after the dosing solution is made. If there is a delay in administration, it

The full-calculated dose will be

administered based on the subject's actual baseline weight measurement in kilograms. Following the first dose, subsequent doses will only be modified if the subject's weight changes by more than 10% from the Day -1 weight at which point it will be recalculated using the current weight.

XmAb18087 should not be administered as an IV push or bolus.

Study drug will be administered as an open-label solution at a constant rate period. Precautions for CRS or infusion reactions or anaphylaxis should be observed during XmAb18087 administration. Due to the possibility that CRS, allergic reactions, or infusion reactions may occur, emergency resuscitation equipment (a "crash cart") and medications including steroids and tocilizumab should be present in the immediate area where subjects are receiving their infusions. Additional supportive measures should be available and may include, but are not limited to: acetaminophen, antihistamines, corticosteroids, IV fluids, bronchodilators, epinephrine, vasopressors, oxygen, and tocilizumab. Please refer to Section 11.3 or Appendix C for management of infusion reactions, CRS, and neurologic toxicities.

Vital signs will be measured and recorded as follows: immediately (within 60 minutes) prior to the infusion; during the infusion at 15, 30, and 60 minutes (± 5 minutes for each time point) from start time of the infusion; immediately (within 5 minutes) before EOI; and at 15, 30, and 60 minutes (± 5 minutes for each time point), then hourly (± 5 minutes) for a 3-hour period, after EOI. Oxygen saturation levels will be captured with each vital sign collection; however, pulse oximetry monitoring must be maintained continuously throughout the entire admission or observation period for each administration of XmAb18087. All supportive measures consistent with optimal subject care will be provided throughout the study according to institution standards. For subjects who a) tolerate 3 consecutive infusions without an infusion reaction during the observation period and b) have completed 4 infusions at the highest dose for that subject, the postinfusion observation period and vital signs assessment may be reduced from 4 hours to 2 hours.

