11.3.3. Treatment Guidelines for Cytokine Release Syndrome

11.3.3.1. Use of Tocilizumab for Cytokine Release Syndrome

Tocilizumab is a therapeutic antibody that interferes with binding of IL-6 to the IL-6 receptor. It has been used to decrease the severity and possibly mortality of severe CRS (Frey, 2017), and early administration may be useful in improving outcomes. Below are suggested guidelines for its use:

Version 1.0 Page 88 of 145

- Sufficient tocilizumab (dose of 8 mg/kg) should be readily available to the area where subjects are receiving their infusions and being observed post infusion.
- Prompt tocilizumab therapy should be strongly considered if:
 - Oxygen saturation falls below 90% on room air, **OR**
 - Systolic blood pressure falls 20 mm Hg below predose measurements and below 100 mm Hg, **OR**
 - Temperature of > 38 °C (100.4 °F) in the presence of new or worsening dyspnea and/or tachypnea and/or rigors and/or tachycardia (heart rate [HR] > 110 bpm), OR
 - Early discovery of hepatic transaminase elevation. (Note that peak transaminase elevation appears to occur within 24 hours, so that it is unlikely that tocilizumab treatment on the day after study drug administration would affect the course or outcome in the absence of concurrent symptoms or signs of CRS).
- Repeat dosing of tocilizumab may be necessary if signs and symptoms persist or return after initial treatment.

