11.3.3.3. Cytokine Release Syndrome Treatment Guidelines by Grade

The following are treatment guidelines for XmAb18087 treatment-related infusion reactions (Lee, 2019); since it can be difficult to differentiate between different infusion reaction etiologies, both are included here.

Grade 1:

- Administer acetaminophen and/or diphenhydramine or dexamethasone to treat signs and symptoms if clinically indicated.
- Vital signs should be measured every 15 minutes or less as clinically indicated.
- Obtain a blood sample for cytokine analysis during the event and approximately 4 hours later, unless to scheduled cytokine monitoring is already in progress.

Version 1.0 Page 89 of 145

- Monitor the subject for worsening of condition; if severity of event increases to a higher grade, stop the infusion, administer appropriate treatment, and refer to guidelines below for more severe infusion reactions.
- It may be useful to premedicate the subject with acetaminophen and antihistamines prior to the next infusion.

Grade 2:

- Hypotension responsive to fluids or a low dose of a single pressor, or mild respiratory symptoms treatable with low-flow oxygen are signs of Grade 2 toxicity. Older subjects or those with significant comorbidities may be at higher risk of decompensation in this situation.
- **Discontinue the infusion** and administer acetaminophen and/or diphenhydramine or dexamethasone to treat signs and symptoms if clinically indicated. Once symptoms have resolved, slow the infusion rate by 50% of the baseline rate. If after 1 hour, the subject's symptoms do not return and vital signs are stable, the infusion rate may be increased every 30 minutes, as tolerated, to the baseline rate.
- Note that older subjects or those with significant comorbidities may be at higher risk of decompensation in this situation. When reactions occur in these vulnerable subjects, or in the case of rapidly escalating reactions, consider treatment with **tocilizumab** 4 to 8 mg/kg IV over 1 hour, with or without dexamethasone 10 to 20 mg IV (or equivalent).
- Vital signs should be measured every 15 minutes or less as clinically indicated. For subjects who are able to tolerate an increase in the infusion rate back to baseline and maintain normal blood pressure for 30 minutes after the rate increase then, at the discretion of the Investigator, the frequency of vital sign assessment may be reduced to every 30 minutes during the infusion.

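### A Table 7 footnote makes vital signs at the Cycle 1 Day 36 infusion depend on an optional hospital stay, against three other provisions that require them on every XmAb18087 infusion day

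*Protocol*

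**What the plan says.** Table 7 marks both XmAb18087 administration and vital signs on Cycle 1 Day 36. The Cycle 1 vital-signs row carries footnotes c, j and k.

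- **Footnote c, on the stay:** "Hospitalization on Days 36 through 39 in Cycle 1 is optional if PK sampling cannot be accommodated as an outpatient".
- **Footnote c, on vital signs:** "Vital sign assessments on Days 36 through 39 in Cycle 1 will be performed only if the subject is hospitalized".
- **Footnote j, on the same row:** "On days of XmAb18087 infusions, vital signs should be taken within 60 minutes of predose", followed by readings during and after the infusion.
- **Section 7.9.3.1** gives the same infusion-day series. It lets the reading just before the end of infusion (EOI) be skipped when it falls at 60 minutes: "immediately (within 5 minutes) before end of infusion (EOI; if different than 60 minutes from start of infusion").
- **Section 10.1.4**, the dosing section, is the firmest: "Vital signs will be measured and recorded as follows: immediately (within 60 minutes) prior to the infusion", and so on through the post-infusion period.
- **Section 7.3**, for Parts A and C: "each cycle will consist of 6 weekly doses of XmAb18087 (on Days 1, 8, 15, 22, 29, and 36"). For Part B it lists XmAb18087 on Days 1, 8, 22, 29 and 36.

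The only relaxation in Sections 7.9.3.1 and 10.1.4 shortens post-infusion observation and vital signs from 4 hours to 2 for subjects who have tolerated earlier infusions. It does not drop them. SAP Section 4.2 refers back to protocol Section 7.9 for the schedule, so it inherits the conflict.

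**The concern.** Footnote c treats Day 36 like Days 37 to 39, but Day 36 is a dosing day and the other three are not. A site that follows the footnote literally can infuse an outpatient with no scheduled temperature, blood pressure, heart rate or respiratory rate before, during or after the infusion.

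Three things depend on those readings:

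- **CRS.** Its incidence and severity form a primary safety endpoint, and so does the incidence of clinically significant vital-sign changes (Section 14.3.1). CRS is graded on fever, hypotension and hypoxia (Table 10). Continuous oximetry covers only hypoxia.
- **The tocilizumab criterion** in Section 11.3.3.1: "Systolic blood pressure falls 20 mm Hg below predose measurements and below 100 mm Hg". It needs a predose value, which footnote c would remove.
- **Reporting.** SAP Section 11.5 lists vital signs at each scheduled time point, and SAP Section 8.2 has protocol deviations listed and discussed. Missing Day 36 vital signs in an outpatient would comply with footnote c and deviate from Section 10.1.4.

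**Working it through.** The plan states no figure to reproduce. The check sets the texts side by side and then counts what is affected.

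**1. Can both rules be followed?**

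| Source | Cycle 1 Day 36, outpatient |
|---|---|
| Table 7 grid | Infusion and vital signs both marked |
| Footnote c | Vital signs not performed |
| Footnote j | Full timed series (infusion day) |
| Section 7.9.3.1 | Full timed series (infusion day) |
| Section 10.1.4 | Full timed series, measured and recorded |

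They cannot, and no precedence rule is given.

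**2. Is it a deliberate exception?** Nothing suggests so. The only reason footnote c gives for the stay is PK-sampling logistics. Section 7.1 requires admission only around the first two doses, yet vital signs are required at the later XmAb18087 infusions in Cycle 1, where no inpatient stay is marked. The Cycle 2 and higher vital-signs row, including its Day 36, does not carry footnote c. Read literally, Cycle 1 Day 36 is the only XmAb18087 infusion that could go without scheduled vital signs.

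**3. Time points lost at that infusion (footnote j).**

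- Full series: 1 predose + 3 after start + 1 before EOI + 3 at 15, 30 and 60 minutes after EOI + 3 hourly = 11.
- If the pre-EOI reading coincides with 60 minutes: 11 − 1 = 10. The infusion duration is redacted, so both cases stay open.
- If observation is cut to 2 hours, the 3-hour and 4-hour readings go: 11 − 2 = 9.
- Both reductions: 11 − 1 − 2 = 8.

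**4. Where the 2-hour reduction could apply, and where Day 36 falls in the dosing (Tables 2 to 4).** The reduction needs 4 completed infusions at the subject's highest dose.

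| Cohort | Dose on Day 36 (µg/kg) | Rank of Day 36 at that dose |
|---|---|---|
| 1A, 1C | 1.0 | 5th |
| 2A, 2C | 2.0 | 4th |
| 3A, 3C | 4.0 | 3rd |
| 1B | 0.3 | 5th |
| 2B | 1.0 | 4th |
| 3B, 4B | 2.0 | 2nd |

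Four infusions at that dose are complete before Day 36 only in Cohorts 1A, 1B and 1C. In no cohort is Day 36 the first infusion at its dose.

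**5. Share of Cycle 1 XmAb18087 infusions.** Parts A and C: 1 of 6. Part B: 1 of 5.

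**6. Upper bound for the subjects enrolled.** SAP Section 5.1 reports 4 subjects, 2 in Part A and 2 in Part C. At most 4 × 1 = 4 infusions and 4 × 11 = 44 time points are affected, or 4 × 8 = 32 if both reductions applied to all. This assumes that all four reached Day 36 as outpatients, which the documents do not state.

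**The case against.** The strongest reply is that this is a one-digit slip. One footnote clause stands against a consistent set of provisions: the Table 7 grid, footnote j, Sections 7.9.3.1 and 10.1.4, the per-infusion summaries in Section 14.6 and the tocilizumab criterion. Harm arises only if a site follows the clause and disregards the dosing section. Footnote c is also attached to the inpatient-status row, so it could be read as governing only the extra readings of a hospital stay. Both points make literal compliance less likely. But the footnote does not limit itself in that way, and nothing else resolves the conflict.

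The safeguards that remain also carry weight. For a Day 36 outpatient these are continuous oximetry, 2 to 4 hours of observation, the examination, ECG and laboratory tests, and cytokine draws to 10 hours after EOI. Once a Grade 1 or 2 reaction begins, the guidance is: "Vital signs should be measured every 15 minutes or less as clinically indicated". That guidance is for sites whose own standards are absent or incomplete (Section 11.3.1). Section 11.3.2 places the higher CRS risk at the first or first escalated dose, and Day 36 is neither. Against that, Section 10.1.3 allows prophylaxis to be reduced after four consecutive reaction-free doses. In Part B, Day 36 is the fifth XmAb18087 dose and could be the first given without full premedication.

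Two points on the figures stand. The bound of 44 is a ceiling, and the true count may be zero. In Cohorts 2A, 2B and 2C, Day 36 is itself the fourth infusion at the top dose. If it counts toward its own post-infusion period, the 2-hour reduction reaches those cohorts too. The range of 8 to 11 is unchanged either way.

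**Conclusion.** The concern holds. For an outpatient on Cycle 1 Day 36, footnote c contradicts footnote j and Sections 7.9.3.1 and 10.1.4, and the plan does not say which prevails. The conflict is confined to that one infusion.

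The effect is a partial gap in safety monitoring and in the completeness of the vital-sign listing. It does not touch sample size or error rates. After early termination the SAP plans listings only, and Part B enrolled no one. The point is still worth correcting, because the report needs a single rule for judging missing Day 36 vital signs and the schedule might be reused. That Days 37 to 39 were meant is an inference.

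**What to change.** In the last sentence of Table 7 footnote c, change the start of the range from Day 36 to Day 37, so that only vital signs on the non-dosing Days 37 to 39 depend on hospitalization. The footnote j series then applies on Day 36 whether or not the subject is an inpatient, subject to the 60-minute overlap and 2-hour reduction already in Section 7.9.3.1. Section 14.6 needs no change.

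The cost is one number in one footnote. No visit is added, because the subject is already on site for the infusion and the observation period.
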